4.12 Outcome measures

Primary outcome measure:	Mortality (all causes) 30 days after randomisation.
Secondary outcome measures:	Mortality rate at first discharge from ICU Mortality rate at first discharge from hospital Mortality rate one year after randomisation Non-pulmonary organ failures whilst treated on an intensive care unit Health-related quality of life six months after randomisation Health-related quality of life one year after randomisation Pulmonary function one year after randomisation Ventilator-free days Antimicrobial-free days Sedative-free days
Primary health care system benefit:	Cost per quality-adjusted life year gained one year after randomisation
Secondary health care system benefits:	Intensive care unit length of stay Hospital length of stay Utilisation of hospital resources after acute hospital discharge one year after randomisation Utilisation of community care resources after acute hospital discharge one year after randomisation

4.13 Data collection

Data related to the primary and secondary outcomes and for long term follow up of patients will be collected in a standardised way onto a trial specific case report form. Copies will be retained at the recruiting centre. Data will be transcribed onto the form from the patients' notes or the clinical information system (CIS) by the team responsible for the patients' care.

Before the study starts, data collection forms will be piloted to determine ease of use and other practical issues.

Patients will be 'flagged' on the Office of National Statistics (ONS) database to ensure reliable collection of the outcome measures. Lists of survivors to hospital discharge will be sent to the ONS regularly were two checks are carried out. The first is list cleaning, which maximises the chances of identifying individual patients on the ONS databases. The second check will reveal any patients who have died after hospital discharge to ensure follow up questionnaires are not posted out to deceased patients. For some patients it may be necessary to contact the patient's general practitioner to obtain the patients status.

The trial office may send self-administered questionnaires to determine health related quality of life (EQ-5D and SF-12 version 2) and specifically respiratory function (St George's Respiratory Questionnaire) to all survivors at six months and one year after randomisation, with follow-up letters one month after the original mailing. These

questionnaires also include questions on social and health service use. Freepost envelopes will be provided. Patients who have died after hospital discharge but prior to the mailing will be identified from the ONS returns and removed from the mailing list.

4.14 Health Economics

Economic analysis will be undertaken to investigate the short and longer term costeffectiveness of HFOV in ARDS patients. Analyses for this study will be undertaken from an NHS perspective. The main health economic outcome will be the health status of survivors of ARDS at 6 months (from EQ-5D data) which will be converted into Quality Adjusted Life years (QALYs) to allow cost-utility modelling. Additionally, a range of modelling techniques will be used to estimate longer-term cost-utility from one year followup data. Epidemiological and economic models will be used to estimate lifetime gains in QALYs from HFOV and savings in health care expenditures. A full literature review will be undertaken to explore the potential for providing monetary estimates of the long term impacts of HFOV. This work will be undertaken at the University of Leeds.

To inform the economic analysis a representative sampling framework for UK ICUs based on size (number of beds), consultant/bed ratio, nurse/bed ratio; and median APACHE II score of admissions will be prepared, and in at least one unit from each cell in the sampling frame we will undertake a micro costing study for patients with ARDS.

A research assistant will visit these units to observe the care patients with ARDS receive and then cost it, along with representative patients not suffering from ARDS. The units will not have to be the same as those recruiting patients to the trial to obtain data on resource use in patients not receiving HFOV. Trial units, and in addition some non-trial ICUs undertaking HFOV, will be used to determine resource use for HFOV in both the trial setting and in the more 'mature' use of HFOV in ARDS.

To provide some estimate of quality of life beyond 12 months, patients recruited in the first year will receive an additional EQ-5D questionnaire and questions concerning social and health service use at 24 and 30 months. The patients recruited in the second year will received an additional EQ-5D questionnaire and questions concerning social and health service use at 18 months. This will allow us to model the time for health-related quality of life to return to population normal levels after ICU by group.

4.15 Sample size

The planned sample size is 802 patients (401 in each arm).

Update October 2009: Section 4.15 to 4.17 details the required sample size (N=1006; with 503 per arm) and how it was planned to achieve this prior to this amendment.

The expected rate of recruitment, as detailed in section 4.17, was just over 2 patients per centre per month. Since 1st December 2007 (start of recruitment) to 1st April 2009, the observed rate of recruitment had averaged to 1.01 per centre per month, approximately half of what was expected and thus the trial was severely under recruiting.

After reviewing various strategies of increasing recruitment with experts in this research field, the Data Monitoring Committee (DMC) and the Trial Steering Committee (TSC), it was agreed that the effect size based on the clinical relevant difference should be re-visited and closely assessed. The original sample size was based on 9% absolute change in mortality and this was obtained from the only study of ventilation in ARDS (the 'ARDSnet' study), which showed a benefit.

The data was un-blinded (at the request of the HTA) and approval to un-blind the control rate mortality has been agreed jointly between the chairperson of the Trial Steering Committee ([name]) and the chair of the Data and Ethics Monitoring Committee ([name]). It was agreed that this information should be shared with the trial statistician and the HTA only. The sample size using a 10% absolute change in mortality was re-calculated, with 80% power and 5 % significance level, suggesting a total of 802 patients (with 401 per treatment arm). This re-calculated sample size was discussed with clinical members of the TSC, who felt this represented a reasonable compromise between an achievable and clinically credible improvement in mortality, and the need to reduce the sample size and hence costs.

4.16 Justification for sample size and details of the power calculation

[See October 2009 update in 4.15 above]

The sample size calculations are based on the primary outcome measure, 30 day allcause mortality. Data are available for all-cause mortality in patients meeting the entry criteria for the proposed study from a number of sources.

Large epidemiological studies of ARDS in Europe have been undertaken at regular interval over the last decade. The most recent is the ALIVE study [15], which collected data from February to March 1999 from 78 ICUs across Europe. Cases of ARDS were identified at any point in their ICU stay using the American-European Consensus Conference criteria. A total of 401 cases of ARDS were identified amongst 6,522 admissions. Hospital mortality was 57.9%, 30 day mortality was not recorded.

These data are robust but are an average across multiple European ICUs, are 7 years old, and the 30 day mortality is not known.

Data collected and analysed by the Intensive Care National Audit & Research Centre (ICNARC) were presented at the US Society of Critical Care Medicine in January 2006. The data came from 261,193 cases admitted to 174 adult, general ICUs in England, Wales and Northern Ireland, from December 1995 to July 2005. Cases were identified using the lowest PaO₂/FiO₂ ratio recorded in the first 24 hours after ICU admission, and categorized into acute lung injury (ALI) and acute respiratory distress syndrome (ARDS) using the American-European Consensus Conference on ARDS definitions [12] but excluding the chest radiograph requirement. Overall (patients with either ALI or ARDS) the hospital mortality was 44%, but only 61% of these patients were artificially ventilated on ICU admission. For those with ARDS who required artificial ventilation at the time of admission the hospital mortality was 42.4%. The 30 day mortality was not presented, median length of hospital stay was 16 days.

The main drawbacks with the ICNARC data are that they only identify patients who meet the study entry criteria in the first 24 hours following ICU admission, they are based on a single blood gas estimation, there is no chest radiograph data, and the quoted mortality is hospital, not 30 day mortality. More details on the limitations of the ICNARC data are given in section 3.5.

We undertook a similar study using data on admissions to the adult ICU at the John Radcliffe Hospital, Oxford, for the calendar year 2005. Of 973 admissions, 850 had simultaneous arterial blood gas analyses and FiO₂ records which allowed PaO₂/FiO₂ ratios to be calculated. The incidence of ARDS, defined using a PaO₂/FiO₂ ratio of less than 23.7kPa at any point during the patient's stay, was 78.9%. However only 2.5% of the patients had both a PaO₂/FiO₂ ratio of less than 26.7kPa and any mention of ARDS in the discharge summary. These patients had a 38% 30 day mortality.

The limitation of the Oxford data is that true incidence of ARDS in ICU patients is almost certainly greater than the 2.5% we identified by retrospectively searching the database of discharge summaries. As a result the mortality estimate may be erroneous.

The Scottish Intensive Care Society Audit Group (SICSAG) published data from 23 of the 26 ICUs in Scotland for an audit run between May and December 1999 [4]. They only recorded patients meeting the diagnostic criteria for ARDS, but unlike ICNARC determined whether patents had ARDS on a daily basis, rather than only on admission, and included chest radiographs in the inclusion criteria. They reported a 61% hospital mortality for patients meeting the ARDS criteria at any point in their ICU stay.

The main drawbacks of the SICSAG data are that they are now 7 years old, and the data are hospital not 30 day mortality.

To calculate the sample size we have assumed that hospital mortality is close to 30 day mortality, and have chosen a middle value from the available data, namely 45%. We have used the effect size from the only intervention known to alter mortality in ARDS [5] as our predicted effect size (9% absolute mortality reduction). This is close to the effect size in the unweighted pooled data from the two RCTs performed to date (8.1% absolute mortality reduction, see figure 1). We know that the loss of patients to the Pac-Man study [45] due to withdrawals was in the order of 3%. Cross-overs will be analysed on an intention to treat basis and so no correction is required. Using an 80% certainty of detecting this difference at $p \le 0.05$ with a control group mortality of 45% requires 503 patients in each arm, a total study size of 1006.

Table 2 gives the reduction (or increase) in mortality detectable with 1006 patients using each of the estimates of hospital mortality. Note that the absolute mortality reduction detectable is insensitive to the mortality estimate used.

Source of estimate	Hospital mortality (%)	Absolute mortality reduction detectable	Relative mortality reduction detectable
ALIVE study	58%	9%	16%
ICNARC	42%	9%	21%
SICSAG	61%	9%	15%
Oxford data	38%	9%	24%

Table 2: Hospital mortality estimates and detectable changes with 1006 patients.

Table 3 gives the sample sizes required for increasing the power of the study.

Table 3: Sample	size calculations fo	or varving power.	p=0.05. control are	oup mortality 45%.
			,	

Power	Total sample size	Sample size allowing for dropouts
80%	976	1006
90%	1290	1330
95%	1584	1632
99%	2220	2288

4.17 Planned recruitment rate

[See October 2009 update in 4.15 above]

Recruiting patients from 12 large UK ICUs admitting at least 650 patients per year each gives a potential pool of patients of 7,800 admissions per annum or 23,400 in the 36 months OSCAR would recruit over. Based on the incidence of ARDS found in Scotland [4] of 8.1%, this would give a potential pool to recruit from of 1895 patients. From previous studies in ICU (the completed Pac-Man study and the ongoing TracMan, PERMIT and SimSepT studies) we know that the refusal rate for consent to research in ICU is approximately 30%. This would leave about 1320 potential patients for the OSCAR study, about 30% more than required. The required recruitment rate is just over 2 patients per month per site.

With a single HFOV ventilator at each site, it will only be possible to recruit when the ventilator is available. No data on the mean duration of ventilation with HFOV are contained in the reports of the RCTs, but in the SICSAG report patients with ARDS have a mean length of ICU stay of 13.6 days. As, even for patients randomised to receive HFOV, a significant proportion of this time will be a weaning phase on conventional ventilation, we predict unavailability of machines will not be a major bar to recruitment.

Adding additional centres to this study to give a greater safety margin for recruitment is very expensive in both equipment and personnel. We are reasonably confident that with local part time study staff, a manageable number of ICUs, and careful central trial management this recruitment is achievable.

4.18 Type of analysis

[name], Senior Statistician at Warwick, will act as trial statistician and perform the analyses. A detailed clinical trial analysis plan will be submitted to the DMEC for approval. Standard approaches will be used to detect patterns in missing data. All analyses will be on an intention to treat basis. For the primary, and other, dichotomous outcomes risk ratios and 95% confidence intervals will be calculated. Time to event outcomes such as duration of ventilation or duration of hospital stay will be analysed using survival methods and reported as hazard ratios and 95% confidence intervals.

4.19 Subgroup and exploratory analyses

Additional analyses will explore:

- The effect of HFOV on length of hospital stay, 30 day and hospital mortality in subgroups with different severity of illness determined by APACHE II scoring on ICU admission.
- The effect of HFOV on length of hospital stay, 30 day and hospital mortality in broad ARDS subgroups (pulmonary or extrapulmonary cause, sepsis, trauma, burns).
- The effect of HFOV on length of hospital stay, 30 day and hospital mortality in patients with differing severity of lung injury determined from their PaO₂/FiO₂ ratio.

4.20 Compliance and crossovers

The primary responsibility for the care of ventilated patients on ICUs passes from one consultant to the next on a daily or weekly basis depending on the type of duty roster. To ensure compliance with the trial protocol throughout a patient's stay, and to avoid cross-over after allocation, units will only be signed up to the trial and given access to an HFOV ventilator, if they agree to use it only for OSCAR patients. Only ICUs where *all* the consultants agree to abide by the protocol will be used as recruiting centres. Centres that use the HFOV ventilator outside of the trial will have the ventilator removed and a new site initiated.

All trial participants will be analysed according to the intention to treat principle. There is no provision in the protocol for cross-over from conventional ventilation to HFOV. Patients who suffer HFOV-specific complications will be placed on conventional ventilation.

4.21 Frequency and timing of interim analyses

The frequency and timing of analyses will be determined by the Data Monitoring and Ethics Committee (DMEC) in line with its Standard Operating Procedures.

5 ORGANISATION

5.1 The Data Monitoring and Ethics Committee (DMEC)

The DMEC will comprise of a senior statistician, a senior clinician, and a senior trialist (Chair), see Appendix 6 for membership details.

Standard Operating Procedures for the DMEC:

- During the period of recruitment into the study, interim analyses of the proportion of patients alive at 30 days and analyses of deaths from all causes at 30 days will be supplied, in strict confidence, to the chairman of the DMEC, along with any other analyses that the committee may request.
- 2) In the light of these analyses, the DMEC will advise the Chairman of the Steering Committee if, in their view, the randomised comparisons have provided both (i) 'proof beyond reasonable doubt' that for all, or some, the treatment is clearly indicated or clearly contra-indicated and (ii) evidence that might reasonably be expected to materially influence future patient management.
- 3) Appropriate criteria of proof beyond reasonable doubt cannot be specified precisely, but the DMEC will work on the principle that a difference of at least 3 standard deviations in an interim analysis of a major outcome event may be needed to justify halting, or modifying, a study before the planned completed recruitment. These criteria have the practical advantage that the exact number of interim analyses would be of little importance, and so no fixed schedule is proposed.
- 4) Following a report from the DMEC, the Steering Committee will decide whether to modify entry to the study (or seek extra data). Unless this happens the Steering Committee and the collaborators will remain ignorant of the interim results.

- 5) Data relating to the safety of patients will be reviewed by the Chair of the DMEC once 50 patients have been randomised to the trial. The data reviewed will specifically relate to:
 - a) procedure related 'serious, unanticipated adverse events' (death or serious disability)
 - b) procedure related adverse events/ complications
 - c) deaths at 30 days (any cause)
- 6) The DMEC will meet to review at one year, or at 100 deaths, whichever occurs first. The DMEC will meet at intervals determined by the DMEC chair.

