4.9.2 Clinical management of patients in the control arm (conventional ventilation)

We will suggest but not mandate that control patients be managed using the current best conventional ventilation strategy. This is limited tidal volume, pressure controlled artificial ventilation using tidal volumes of 6-8ml kg⁻¹ body weight.

FiO2	PEEP
0.3	5
0.4	5
0.4	8
0.5	8
0.5	10
0.6	10
0.7	10-14
0.8	12-14
0.9	12-16
1.0	12-18

We recommended the following combinations of FiO₂ and PEEP:

This ventilation strategy is normal practice in most UK ICUs.

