4.10.1 What is a SAE

A SAE is an *untoward* and *unexpected* occurrence that a research participant experiences which:

- i Results in death
- ii Is life threatening
- iii Requires hospitalisation or prolongation of existing hospitalisation
- iv Results in persistent or significant disability or incapacity
- v Consists of a congenital anomaly or birth defect.

4.10.2 Reporting a SAE:

An SAE must be recorded on the appropriate trial form by the clinician caring for the patient and reported locally immediately to the Principal Investigator at that centre. The Principal Investigator will then report the SAE to the Chief Investigator of the OSCAR trial, [name], within 3 working days of the event:

[name], Chief Investigator, OSCAR Trial Office, Kadoorie Centre for Critical Care Research and Education, John Radcliffe Hospital, [name]. [contact], [contact], Email: [contact].

[name] will give an opinion as to whether the event is:

- 'related' (resulted from administration of any of the research procedures), and
- 'unexpected' (the type of event is not listed in the protocol as an expected occurrence).

A confirmed, related, SAE will be submitted to a Main Research Ethics Committee within 15 days of the Chief Investigator becoming aware of the event using the NRES report of serious adverse event form.

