4.11 Expected events

Most known events related to artificial ventilation will occur equally in both groups. Exceptions that might occur more frequently in the HFOV group are:

- 1) Air trapping
- 2) Secondary effects of air trapping such as reduced carbon dioxide clearance.

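### The early safety review admits non-fatal harms only if 'procedure related', a term not defined by arm, so the same ventilator complication may count on HFOV and not on conventional ventilation

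*Protocol*

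**What the plan says.** Section 5.1, item 5, provides that safety data will be "reviewed by the Chair of the DMEC once 50 patients have been randomised to the trial". It names three kinds of data:

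- (a) "procedure related 'serious, unanticipated adverse events' (death or serious disability");
- (b) "procedure related adverse events/ complications";
- (c) "deaths at 30 days (any cause").

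Only (c) carries no causality condition. Item 5 does not say what 'procedure' means in each arm, or who decides.

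The nearest definition is in section 4.10.2. There the Chief Investigator gives an opinion on whether an SAE is related, meaning that it "resulted from administration of any of the research procedures". Section 4.1 describes the trial as open. Section 4.9.2 suggests but does not mandate the control strategy, and says of it: "This ventilation strategy is normal practice in most UK ICUs". Section 4.11 states: "Most known events related to artificial ventilation will occur equally in both groups". It names air trapping and its secondary effects as possible exceptions on HFOV.

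**The concern.** A causality filter is neutral between arms only if it is applied alike in both. Here the new technique is easily seen as the research procedure, and control ventilation as usual care. A complication on HFOV then tends to be called procedure related, while the same complication on conventional ventilation may be put down to routine treatment or the underlying illness. The judgement is made by people who know the allocation.

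Two things are at stake. Equal true rates could look like an HFOV excess. A real HFOV excess could also not be told apart from an effect of attribution, because the control count needed for comparison was not built on the same rule. Section 4.11 rests on just that comparison.

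**Working it through.** The plan states no figure on this point, so there is none to reproduce. The check is of the text, followed by an illustration.

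**Text, side by side**

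1. Section 5.1, item 5: non-fatal events enter the review only under (a) or (b), and both are filtered.
2. Section 4.10.2: relatedness refers to research procedures, which are not listed by arm.
3. Section 4.9.2: control ventilation is not mandated and is described as normal practice. Section 5.13.2: most units will not have used HFOV before. Attribution to HFOV is therefore the easier call.
4. Section 4.10.1 makes an SAE an unexpected event, and item 5(a) covers unanticipated events only. The expected complications in section 4.11, such as air trapping, fall outside both. Item 5(b) is the only named route by which they reach the DMEC.
5. Section 4.12 lists non-pulmonary organ failures and ventilator-free days, but no ventilator or pulmonary complication, so the outcome list does not fill the gap.

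**Illustration**

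Inputs from the protocol: 50 patients (5.1) and 1:1 allocation (3.3), hence about 25 per arm; equal true rates (4.11). Assumed, because the protocol gives no figures: a true complication rate t in both arms, and shares a (HFOV) and b (control) of complications that are judged procedure related.

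- Expected counts shown to the reviewer: 25·t·a on HFOV and 25·t·b on control.
- Apparent risk ratio: (t·a)/(t·b) = a/b, whatever t is.
- P(HFOV count > control count): from two independent binomials, Bin(25, t·a) and Bin(25, t·b).

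| a, b | Apparent ratio | Expected counts, t = 20% | P, t = 10% | P, t = 20% | P, t = 30% |
|---|---|---|---|---|---|
| all events counted | 1.0 | 5.0 v 5.0 | 0.41 | 0.43 | 0.44 |
| 0.9, 0.50 | 1.8 | 4.5 v 2.5 | 0.61 | 0.73 | 0.81 |
| 0.9, 0.25 | 3.6 | 4.5 v 1.25 | 0.76 | 0.90 | 0.96 |
| 0.9, 0.10 | 9.0 | 4.5 v 0.5 | 0.85 | 0.97 | 0.99 |

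For example, with t = 0.20, a = 0.9 and b = 0.5: 25 × 0.20 × 0.9 = 4.5, 25 × 0.20 × 0.5 = 2.5, and 0.9/0.5 = 1.8. If 'procedure' is read as ventilation in either arm and applied equally, a = b and the ratio is 1.0. The table shows how the mechanism works; it does not estimate what happened.

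**Timing**

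Section 4.15 gives 1.01 patients per centre per month from 1 December 2007 to 1 April 2009, which is 16 months, so 1.01 × 16 = 16.2 per centre. Fifty patients need 50/16.2 ≈ 3.1 centres recruiting throughout, and section 4.3.1 plans for ten or more. This protocol version is dated June 2011, so the 50-patient review has very probably taken place. Appendix 9 has recruitment continuing to the end of July 2012.

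**The case against.** The strongest reply is that 'procedure' need not mean HFOV. Section 4.10.2 speaks of research procedures in the plural, section 4.5 lists conventional ventilation as a randomised arm begun after randomisation, and section 4.11 links known events to artificial ventilation in both groups. Read that way the filter is symmetric. This stands as a possible reading, and it is why the point is a risk only. It does not remove the ambiguity, which remains open in an unblinded trial.

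A reader might also infer that control-arm SAEs go unrecorded. The protocol does not support this: under section 4.10 an SAE in any participant is recorded and reported up to the Chief Investigator, and relatedness is judged only then, as the condition for ethics-committee submission. Nor is the treating clinician assigned that judgement.

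It is tempting, too, to infer that HFOV-arm events drop out after a change of ventilator, since "Patients who suffer HFOV-specific complications will be placed on conventional ventilation". Nothing says that attribution ends with the change, and sections 4.18 and 4.20 require analysis by intention to treat.

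Finally, item 1 of section 5.1 lets the DMEC request other analyses, and the only numerical benchmark (item 3) is 3 standard deviations on a major outcome event, so no stated rule acts on complication counts. Over-counting HFOV harm is also the cautious direction. These points limit the consequence. They do not make a common count part of the review, and a request cannot recover complications that were not recorded alike in both arms.

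**Conclusion.** The point holds as a risk of differential attribution in what item 5 tabulates, mainly the complications under 5(b). It rests on the open design, an undefined term, and the contrast between a new technique and an unmandated usual-care control. A reader might go further and conclude that the harm comparison given to the DMEC is biased by arm. The protocol does not show that: the term can be read symmetrically, and the case report form is not shown. The size cannot be derived from the protocol. The ratios of 1.8 to 9.0 follow entirely from assumed attribution shares, and the ratio is 1.0 under equal attribution. This is an inexpensive improvement to safety monitoring and does not bear on the primary mortality comparison or on all-cause deaths in item 5(c).

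**What to change.** Reword section 5.1, items 5(a) and 5(b), and apply the same rule to later DMEC reports and the final harms table:

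- tabulate all recorded SAEs, and a short prespecified list of ventilation complications chosen by the investigators that includes at least those in section 4.11;
- record the list on the same form in both arms, over one common window starting at randomisation;
- present counts by allocated arm regardless of attribution or of the ventilator in use at the time;
- show relatedness as an added column, and keep it as the trigger for ethics-committee reporting only, as section 4.10.2 already does for SAEs.

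The cost is a wording change, a few extra form items per patient and a longer DMEC table. No treatment rule changes. Because the 50-patient review has probably passed, the benefit falls on later reviews and final reporting. For patients already randomised, complications can be tabulated this way only as far as the existing forms or notes hold them.
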